- e. Slit-Lamp examination of the planned study eye, prior to the sizing and dilation of the lower punctum
- f. Tear lake evaluation of the planned study eye, prior to the sizing and dilation of the lower punctum
- g. Size evaluation of the lower puncta of the planned study eye, prior to dilation of the lower punctum
- h. After dilation of the punctum to at least 1.0 mm, insert the study punctal plug
- i. Inspection of the punctal plug after insertion via slit-lamp
- j. Record any Adverse Device Events
- k. After a study subject has been inserted with the NDE L68 StableFit® punctal plug, the Investigator will evaluate the insertion characteristics of the punctal plug

NOTE: After the last study subject has been inserted with a study punctal plug, based on all subjects enrolled in the study, the investigator will give an overall assessment on the insertion characteristics of the study punctal plug.

Visit 2: Follow-up (Day 7 + 1 post plug insertion)

- a. Verify a subject has not used any ocular drops, in their study eye, within the last hour prior to their scheduled visit
- b. Slit Lamp examination
- c. Inspection of the plug via slit-lamp
- d. Tear lake evaluation
- e. Record any Adverse Device Events

Visit 3: Follow-up (Day 28 + 4 post plug insertion)

- a. Verify a subject has not used any ocular drops, in their study eye, within the last hour prior to their scheduled visit
- b. Investigator evaluation of the subject's acceptability of the punctal plug, prior to removal of the study plug
- c. Slit Lamp examination, prior to removal of the study plug
- d. Inspection of plug via slit-lamp, prior to removal of the study plug

- e. Tear lake evaluation, prior to removal of the study plug
- f. Remove study punctal plug
- g. After the plug has been removed, the Investigator will evaluate the removal characteristics of the inserted punctal plug
- h. Record any Adverse Device Events

NOTE: After the last study subject has had their punctal plug removed, based on all subjects that completed the study, the investigator will give an overall assessment on the removal characteristics of the punctal plug.

Study Outcome Variables:

Primary Study Endpoint: Investigators' evaluation of the tear lake

Secondary Study Endpoint: Investigator's evaluation of epiphora, insertion/ removal characteristics and Investigators' evaluation of the subject's acceptance of the NDE L68 StableFit® punctal plug.

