4.2.1 Primary Study Endpoint

The primary study endpoint will be the comparison of the tear lake volume at baseline with the tear lake volume at each follow-up visit.

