6.5 Punctal Plug – Unable to Insert / Extruded

6.5.1 Unable to Insert a Punctal Plug in Either Punctum

If a punctal plug cannot be inserted in to each eye after dilation, the study subject will be discontinued from the study and replaced.

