7.3 Study Visit Schedule

7.3.1 Visit 1: Day 0 - Screening (Prior to punctal plug insertion)

A potential study subject qualifications will be assessed according to the inclusion/exclusion criteria listed in the protocol (see Sections 5.2 and 5.3). Prior to undergoing any study-specific procedures, both the study Informed Consent and Authorization for Use/Disclosure of Health Information forms (HIPAA authorization) must be signed by a potential subject who has agreed to participate in the study. During this visit, the following information will be collected/evaluated and recorded in the appropriate sections of the study case report forms of a subject, prior to the sizing and dilation of the lower punctum for the planned study eye.

- a. Obtain informed consent and HIPAA authorization release
- b. Record the subject's demographic data and prior 7 days medical history
- c. Verify a subject has not used any ocular drops within the last hour prior to their baseline visit
- d. Record any subject reports of ocular signs or symptoms they are currently experiencing
- e. Slit-lamp examination of the planned study eye

7.3.2 Visit 1:Baseline - Day 0 (Insertion of a punctal plug - refer to Section 6.2 for details regarding the insertion of the NDE punctal plug)

After the screening examination, a qualified study subject will be sequentially assigned an ID number. In addition, the ID number and the study subject initials will be recorded on study case report forms, in lieu of recording his/her name, in order to maintain subject confidentiality.

Note: The investigator has the option of inserting the plug in either the left or right eye of the subject. However, if the investigator is unable to insert the plug in the first eye chosen, the investigator can insert the plug in the fellow eye as long as the fellow eye meets all study inclusion/exclusion criteria.

- f. Tear lake evaluation of the planned study eye prior to the sizing and dilation of the lower punctum
- g. Size evaluation of the punctum of the planned study eye prior to the dilation of the lower punctum
- h. After dilation, the study punctal plug is inserted in to the lower punctum of study eye, inspect the punctal plug using the slit-lamp, the position of a study punctal plug may be adjusted with forceps.
- i. Record any reported adverse device event(s)

j. After the study plug has been inserted in the lower puncta, the investigator will assess the insertion characteristics of the plug.

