10.4.2 Analysis of the Primary Endpoint(s)

The primary study variable will be based on the change from baseline in tear lake values. For analyses, using the intent-to-treat (ITT) data set, all data from all subjects with at least one follow-up evaluation of the tear lake will be evaluated. For the per protocol (PP) analyses dataset, data from subjects or visits with significant protocol deviations will be excluded.

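### After a switch to the fellow eye, no Visit 1 step clearly requires a baseline tear lake reading in the eye that gets the plug; separately, the synopsis and Section 5.3 disagree on which eye five exclusions cover

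*Combined protocol and SAP*

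**What the plan says.** **Baseline.** Section 7.3.2 step f calls for "Tear lake evaluation of the planned study eye prior to the sizing and dilation of the lower punctum"; step f of Visit 1 in the synopsis says the same. The other Visit 1 examinations are framed alike: Section 7.3.1 step e is "Slit-lamp examination of the planned study eye", and the synopsis step g is "Size evaluation of the lower puncta of the planned study eye, prior to dilation of the lower punctum".

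**Switch.** The note in Section 7.3.2, also in the synopsis under Study Design, says that "if the investigator is unable to insert the plug in the first eye chosen, the investigator can insert the plug in the fellow eye", provided that eye meets the eligibility criteria. A failed first eye does not end participation. Section 6.5.1 says: "If a punctal plug cannot be inserted in to each eye after dilation, the study subject will be discontinued from the study and replaced".

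**Endpoint and analysis.** Section 4.2.1 defines the primary endpoint as the "comparison of the tear lake volume at baseline with the tear lake volume at each follow-up visit". Section 10.4.2 says: "The primary study variable will be based on the change from baseline in tear lake values". Its ITT rule takes in every subject with at least one follow-up tear lake value and sets no baseline condition. Neither section says which eye supplies the baseline.

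**Exclusions.** In the synopsis, exclusions a, c, d, e and g are limited to the planned study eye. In Section 5.3 the same five refer to either eye. Exclusion j covers trials of an investigational medication in the synopsis and any other clinical trial in Section 5.3. Section 7.3.1 tells sites which list to use: "A potential study subject qualifications will be assessed according to the inclusion/exclusion criteria listed in the protocol (see Sections 5.2 and 5.3".

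**The concern.** Change from baseline means something for a plug only if both readings come from the eye that holds it. Visits 2 and 3 read that eye. The listed Visit 1 steps guarantee a reading only in the eye first chosen, and the protocol expects that some insertions will be hard: Section 6.2 discusses small puncta, re-dilation and repeated attempts.

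A baseline missed before insertion cannot be recovered. A switch is not a listed ground for replacement in Sections 5.5, 5.5.1.2, 5.5.1.3 or 6.5.1, so the subject would stay in the study without a usable primary observation. The analyst would then have to choose, after the fact, between dropping the subject and subtracting one eye's baseline from the other eye's follow-up.

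The exclusion conflict has its own consequence. A subject acceptable under the synopsis can be an improper entry under Section 5.3. That leads to disqualification and replacement under Section 5.5.1.3 and possible removal from the primary population under Section 10.1.

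**Working it through.** **Part 1: does any text require a tear lake reading in the fellow eye?**

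- *Steps e to g at Visit 1:* slit lamp, tear lake and sizing all name the planned study eye. Step h of Section 7.3.2, the insertion, refers to the study eye. The change of term is not explained.
- *Eligibility condition on the switch:* exclusion d (lid, conjunctival and corneal findings) and exclusion e (punctum size) cannot be judged in the fellow eye without a slit-lamp examination and sizing, so the condition implies both. No inclusion or exclusion criterion uses tear lake height, so it does not imply the tear lake reading.
- *Schedule of Assessments, key B:* names no eye and asks only that the reading precede insertion. Step f is stricter: before sizing and dilation. Under Section 7.2.1 f, sizing involves topical anesthetic and a dilator in the punctum, so a reading taken after sizing would satisfy key B but not step f.
- *Section 7.2.1 e:* describes the measurement, to 0.1 mm, without naming an eye.
- *Section 10.4.2:* admits a subject on a follow-up value alone.

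No text therefore clearly requires the primary measurement in the eye that ends up with the plug.

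**Size, illustrative.** The plan has no figure to reproduce: Section 10.5 makes no sample size calculation, and no switch rate or SD is given. Inputs: N = 40 (Section 4.2), two-sided 5% level (Section 10.4.1), assumed switch rates of 5%, 10% and 20%, and every switched subject lacking a same-eye baseline.

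Subjects lost = rate × 40. The 95% CI half-width for the mean change, in SD units, is t(0.975, n−1)/√n.

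| Switch rate | Lost | n | Half-width (SD) | Widening |
|---|---|---|---|---|
| 0% | 0 | 40 | 0.3198 | – |
| 5% | 2 | 38 | 0.3287 | 2.8% |
| 10% | 4 | 36 | 0.3384 | 5.8% |
| 20% | 8 | 32 | 0.3605 | 12.7% |

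If only some switched subjects lack the reading, the loss shrinks in proportion. At 20% switched with half lacking it, 0.20 × 0.5 × 40 = 4 are lost, which is the 5.8% row.

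**Part 2: the two exclusion lists.**

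| Exclusion | Synopsis | Section 5.3 |
|---|---|---|
| a, c, d, e, g | planned study eye | either eye |
| h | either eye | either eye |
| b, f, i | no eye named | no eye named |
| j | investigational-medication trials | any other clinical trial |

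Five of ten exclusions differ on eye, and a sixth differs on scope. Section 7.3.1 applies Section 5.3, yet the listed slit-lamp and sizing steps cover one eye. When no switch occurs, no listed step documents exclusions d and e for the other eye.

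**The case against.** The strongest reply is that the fellow eye becomes the planned study eye at a switch, so steps e to g attach to it. The placement of the note before steps f to h fits that reading. So does the count of 40 subjects as 40 eyes in Section 4.2, which suggests same-eye pairing. The reading is plausible and many sites would probably follow it. It is not written down, however, and this is the primary measurement.

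A reader might infer that the fellow eye could receive a plug with no examination at all. The documents do not support that: the eligibility condition implies slit lamp and sizing. The gap is the tear lake reading alone.

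A reader might also infer that switched subjects necessarily lack a baseline, or that the primary result would be biased. Neither follows. A site may take the reading, and nothing in the documents gives a direction for any error. A missing value would also be visible, because Section 7 requires missing data to be explained and Section 9 has the monitor check for omissions. Those controls reveal the loss but do not restore the reading.

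On the exclusions, Section 7.3.1 does identify Sections 5.2 and 5.3 as the operative text, which limits the practical harm. It does not settle the mismatch between the either-eye wording and the one-eye examinations.

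Finally, the population is described in three ways: with dry eye (synopsis), with or without it (inclusion a) and as healthy volunteers (Section 5.1). This could be read as an eligibility conflict. It is editorial: inclusion a treats dry eye identically in both lists, and Section 5.1 defers to the criteria.

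**Conclusion.** Both parts stand, at minor to moderate severity.

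Part 1 (medium confidence, because the re-designation reading is available): the plan does not clearly require a same-eye tear lake baseline after a switch and does not define which reading is baseline. The loss of 2 to 8 of 40 observations, with an interval about 3% to 13% wider, is an upper bound. It rests on assumed switch rates of 5% to 20% and on every switched subject lacking the reading. In a pilot without a sample size claim this is a modest loss of precision. The case for acting is that the reading is cheap and cannot be recovered later.

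Part 2 (high confidence): the two exclusion lists contradict each other on six items, and the Visit 1 examinations do not match the list that sites are told to use. This can change who is eligible or disqualified. It has no numeric estimate.

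**What to change.** 1. At Visit 1, read the tear lake in both eyes before any anesthetic, sizing or dilation. Repeating the reading only when a switch occurs is a weaker fallback, because it would follow anesthetic and attempted dilation in the other eye and may not be an undisturbed baseline.
2. In Section 10.4.2, define baseline as the pre-procedure reading in the eye that received the plug, rule out pairing across eyes, and state how a subject without that reading is handled.
3. Record which eye received the plug, and report the number of subjects switched.
4. Reconcile the synopsis with Section 5.3 to one eye scope and one exclusion j, and make the listed Visit 1 examinations match. The choice of scope is the sponsor's. Align the population statements at the same time.

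The cost is one extra slit-lamp micrometer reading per subject and an IRB-approved amendment under Section 7.1, with no added visits. If the either-eye scope is kept, documenting exclusion e would mean sizing the second punctum, which under Section 7.2.1 f involves topical anesthetic in that eye. The sponsor should weigh that when choosing.

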7.3.3 Visit 2: Follow-Up (Day 7 + 1 post plug insertion)

At this visit the following will be performed and recorded:

- a. Verify a subject has not used any ocular drops, in their study eye, within the last hour prior to their scheduled visit
- b. Slit-lamp examination of the study eye
- c. Inspection of the punctal plug via the slit lamp
- d. Tear lake evaluation of the study eye
- e. Recording of any reported adverse device event(s)

7.3.4 Visit 3: Follow-Up (Day 28 + 4 post plug insertion)

At this visit the following will be performed and recorded:

- a. Verify a subject has not used any ocular drops, in their study eye, within the last hour prior to their scheduled visit
- b. Investigator evaluation of subject's acceptability of the punctal plug, prior to the removal of the punctal plug
- c. Slit-lamp examination, prior to the removal of the punctal plug
- d. Inspection of the punctal plug via the slit lamp, prior to removal of the plug
- e. Tear lake evaluation of the eye prior the removal of the punctal plug
- f. Removal of the punctal plug (refer to [Section 6.6](#) for details regarding the removal of a punctal plug)
- g. Recording of any reported adverse device event
- h. After removal of the study subject punctal plug, the investigator will assess the removal characteristics of the plug.

NOTE: After the last study subject has had their punctal plug removed, the investigator will give an overall assessment on the removal characteristics of all punctal plugs that were inserted during the study.

An exit form will be completed at the final study examination (Visit 3), or whenever the study subject completes or leaves the study for any reason.

Schedule of Assessments, Events

EXAM PARAMETERS	v1	v2	v3
Inform Consent/HIPAA	①		
Demographic Data/Medical Hx	① A		
Subject Reports of any Ocular Signs or Symptoms	① B		
Verify No Ocular Drop use One Hour Prior to Visit	①	②	③
Inv. Evaluation of Subject's Acceptance of Study Plug			③ C
Slit Lamp Examination	① B	②	③ C
Tear Lake Evaluation	① B	②	③ C
Size Evaluation of Lower Puncta, Prior to Dilation	① B		
Dilation of Lower Puncta	①		
Insertion of a Punctal Plug	①		
Inspection of the Placement of the Punctal Plug	① D	②	③ C
Investigator Device Assessment of Insertion	① E		
Removal of Punctal Plug			③
Investigator Device Assessment of Removal			③ F
Adverse Device Event Recording	①	②	③

Keys to Abbreviations:

- A = Record medical history for the past 7 days
- B = PRIOR to **INSERTION** of punctal plug
- C = PRIOR to **REMOVAL** of punctal plug
- D = Slit-Lamp Evaluation of Punctal Plug **AFTER INSERTION**
- E = After EACH Study Subject and after **ALL** Study Subjects have had their Punctal Plug Inserted
- F = After EACH Study Subject and after **ALL** Study Subjects have had their Punctal Plug Removed

Visit Schedule:

- v1 = Screening/Baseline
- v2 = 7 ± 1 days post plug insertion
- v3 = 28 ± 4 days post plug insertion

7.3.5 Early Exit

Any study subject exiting the study early, the Investigator must record/perform the following:

- a. Verify a subject has not used any ocular drops, in their study eye, within the last hour prior to their scheduled visit
- b. Investigator evaluation of subject's acceptability of the punctal plug, prior to the removal of the punctal plug, if the plug has not been extruded
- c. Slit-lamp examination, prior to the removal of the punctal plug, if the plug has not been extruded

- d. Inspection of the punctal plug via the slit lamp, prior to removal of the plug, if the plug has not been extruded
- e. Tear lake evaluation of the study eye prior the removal of the punctal plug, if the plug has not been extruded
- f. Removal of the punctal plug (refer to [Section 6.6](#) for details regarding the removal of a punctal plug), if the plug has not been extruded
- g. Recording of any reported adverse device event(s)
- h. After a study subject has had the punctal plug removed, the investigator will assess the removal characteristics of the plug.

An exit form will be completed whenever the study subject completes or leaves the study for any reason.

A study subject that has exited the study due to an adverse device event will be followed by the investigator until the ADE has resolved or has become medically stable.

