5.5 Study Subject Withdrawal or Termination Criteria

After insertion of a study plug, the Investigator may withdraw a study subject from the study if in their medical judgment it is in the study subject's best interest.

Each study subject will be informed that they are free to withdraw from the study at any time. If a study subject is prematurely withdrawn from the study, the reason(s) for withdrawal must be recorded on the relevant page of the subject's case report form (CRF). Study subjects who withdraw from the study will be replaced.

The Investigator, the Investigator in consultation with the Medical Monitor, or the Medical Monitor may exercise his or her medical judgment to terminate a study subject's participation in the study if it is in the best interest of the study subject. A terminated study subject will be followed through Visit 3 (28 days after insertion of the punctal plug) or until the condition has resolved or has become medically stable.

Medical Monitoring for this study will be conducted by:

[name]

Phone (Office): [contact]

Phone (Cell): [contact]

Email: [contact]

The name of the Medical Monitor and contact information will be provided to each study site.

Mati Therapeutics Inc. reserves the right to terminate the study at any time. Every effort will be made to collect all data required by the protocol during or following the termination of a study subject.

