6.5.2 Extrusion of the Punctal Plug after the Baseline Visit

A study subject that has noticed a plug has been extruded or lost during the follow-up period should immediately contact the Investigator and/or his/her staff and return to the Investigator's office as soon as possible. The Investigator will terminate the study subject from the study and will NOT be replaced.

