8.6.4 Anticipated Adverse Device Events

Due to the duration of the study, the only anticipated ADE would be extrusion of the punctal plug. Any event that is unlikely but anticipated must have an adverse device event form completed and reported to Mati Therapeutics Inc. (see [Section 8.5](#) for reporting details).

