10 STATISTICAL CONSIDERATIONS

10.1 Statistical and Analytical Plans

The primary analysis population will be an ITT (Intent-to-Treat) analysis for all study subjects who had a lower puncta inserted with a study punctal plug and had no major protocol violations. Individual study subjects or individual visits may be excluded if a major protocol violation occurs (such as violation of inclusion/exclusion criteria or non-compliance with protocol requirements that can potentially have significant impact on study outcomes).

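### The early-exit visit waives the tear lake reading after an extrusion, so the ITT-labelled primary analysis can lose inserted subjects because their plug failed, depending on when the loss is noticed

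*Combined protocol and SAP*

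**What the plan says.** All references are to the combined protocol and SAP.

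- **Handling of extrusion.** A subject who notices a lost plug returns to the office. Section 6.5.2 then states: "The Investigator will terminate the study subject from the study and will NOT be replaced". Section 5.5.1.1 counts terminated subjects as having completed the study and describes their return visit as a safety evaluation.
- **Exit reading.** Section 7.3.5, item e: "Tear lake evaluation of the study eye prior the removal of the punctal plug, if the plug has not been extruded". Items b, c, d and f carry the same condition.
- **Later follow-up.** Section 5.5: "A terminated study subject will be followed through Visit 3 (28 days after insertion of the punctal plug) or until the condition has resolved", with medical stability as a further end point. No tear lake reading is named there.
- **Scheduled readings.** Section 7.3.3, item d, lists "Tear lake evaluation of the study eye" with no condition on the plug. Section 7.3.4, item e, places the Visit 3 reading before plug removal and has no extrusion clause.
- **Primary endpoint.** Section 4.2.1: "comparison of the tear lake volume at baseline with the tear lake volume at each follow-up visit".
- **Populations.** Section 10.1 takes "all study subjects who had a lower puncta inserted with a study punctal plug", provided there was no major protocol violation. For the primary endpoint, section 10.4.2 says of the ITT set that "all data from all subjects with at least one follow-up evaluation of the tear lake will be evaluated". The PP set removes subjects or visits with significant deviations.
- **Expectation.** Section 8.6.4: "Due to the duration of the study, the only anticipated ADE would be extrusion of the punctal plug".

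The plan gives no extrusion rate, no imputation rule, no rule assigning an exit reading to a visit, and no rule on plug status in the primary analysis.

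**The concern.** Section 10.1 describes an all-inserted population. The data needed to analyse it are not required for the subjects whose device has failed. Section 10.4.2 then works as an available-data rule: a subject with no follow-up reading has no change from baseline and drops out. Extrusion is not described as a protocol violation, so section 10.1 gives no ground for leaving that subject out, and the PP set does not separate plug-in from plug-out eyes.

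Extrusion is the one device event the plan expects, so this is the foreseeable route to missing primary data, and the missingness is linked to the outcome. Section 2.1 says the plug works by physical occlusion, so an eye without its plug may well have a different tear lake. Section 10.4.4 reports the extrusion rate separately, but an all-inserted change cannot be rebuilt from that rate if the readings were never taken.

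**Working it through.** **Step 1. Follow one lost plug through the text.**

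| When the loss is noticed | Reading required | Result in the primary analysis |
|---|---|---|
| Before Visit 2 | None (7.3.5e waives it) | In the 10.1 population, out of the 10.4.2 set |
| Between Visits 2 and 3 | Day 7 reading already taken, plug in; exit reading waived; 5.5 names none | In the set with Day 7 only; no clearly required Day 28 value |
| First found at Visit 2 or Visit 3 | Unsettled | An off-plug value may or may not enter |

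The third row is unsettled for this reason. The scheduled lists carry no extrusion waiver, which suggests that the reading is taken. But both lists put plug inspection before the tear lake reading, and the Visit 3 item presupposes a plug still to be removed. A site could therefore find the loss, terminate under 6.5.2 and apply the early-exit waiver.

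**Step 2. Inputs for an illustration.** The plan has no figure to reproduce: it states no extrusion rate, effect size or SD, and section 10.5 gives no sample size calculation.

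- From the plan: a maximum of 40 eyes (section 4.2).
- Assumed: share lost p = 0.05, 0.10 or 0.20 (2, 4 or 8 eyes); on-plug mean change d; share k of d kept after loss; share r of lost eyes with no Day 28 reading.

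**Step 3. Formulas.**

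- All-inserted mean = d[(1 − p) + pk]
- Available-data mean = d[(1 − p) + p(1 − r)k] / (1 − pr)
- Overstatement = available-data mean / all-inserted mean − 1

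**Step 4. Day 28 results.**

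| Assumption | 2 lost | 4 lost | 8 lost |
|---|---|---|---|
| k = 0, r = 1 (back to baseline, none read) | 40/38 = 1.053 | 40/36 = 1.111 | 40/32 = 1.250 |
| k = 0, r = 0.5 (half read) | 1.026 | 1.053 | 1.111 |
| k = 0.5, r = 1 (half the gain kept, none read) | 1/0.975 = 1.026 | 1/0.95 = 1.053 | 1/0.90 = 1.111 |
| r = 0 (all read) | 1.000 | 1.000 | 1.000 |

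In the first row n falls to 38, 36 or 32.

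**Step 5. Day 7.** If half of those losses are reported before Visit 2 (1, 2 or 4 eyes) and k = 0, the ratios are 40/39 = 1.026, 40/38 = 1.053 and 40/36 = 1.111.

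**Step 6. Null cases.** With no extrusions every ratio is 1. If the plug does not change the tear lake (d = 0), both means are zero and there is no bias in this model.

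**The case against.** The strongest reply is that the waiver suits the question. The objective is the plug's effect on the tear lake, the mechanism is occlusion, and an eye without a plug tells us little about that. The study is a single-arm, open-label pilot, so there is no randomised comparison to protect. Extrusions are counted as a safety endpoint and those subjects are not replaced. If sites apply the waiver at Visits 2 and 3 as well, every analysed reading is on-plug. This much stands: a plug-in-place target is legitimate, and the larger mean is an overstatement only against the all-inserted mean. But the plan labels the analysis ITT and defines it by insertion. Even under a uniform waiver, a loss noticed by Visit 2 leaves the set while a later one stays in through its Day 7 value.

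Second, the plan urges completeness: section 5.5 asks for every effort to collect required data, section 5.5.1 wants early-exit observations as thorough as possible, and section 7 asks for missing data to be explained. None of these makes a waived reading a required one. Item e could also be read as conditioning only the timing of the reading, but its neighbours use the same clause as a plain waiver.

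Third, the percentages are wholly assumed, and section 2.1 claims better retention than marketed plugs, without giving a rate. That is fair. Losses could be few or none.

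A reader might infer that the plan certainly mixes on-plug and off-plug eyes in one mean. The documents do not support that, because the handling of a loss first found at a scheduled visit is open. Nor do they show that the primary test is invalid: no effect on it has been demonstrated.

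**Conclusion.** The point holds as an inconsistency between data collection and the stated population. Section 10.1 includes inserted subjects whom sections 7.3.5 and 10.4.2 together can leave without an analysable value. Whether and how they count depends on when the loss is noticed, and the readings are missing because the device failed.

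The size cannot be known from the documents. The 5%, 11% and 25% figures assume 2, 4 or 8 losses of 40, a full return to baseline and no off-plug reading at Day 28. They shrink if some gain is kept or some eyes are read, and vanish if all are read or no plug is lost. They should not be taken as a forecast of bias, and the documents do not make all-inserted the only defensible target. In a pilot with no sample size basis this is a cheap improvement worth making. No figure stated in the plan is wrong.

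**What to change.** 1. In 7.3.5, delete the extrusion condition from item e, so that the tear lake is read at the exit visit already required. Where the subject is still being followed under 5.5, read it at Visit 3 too.
2. Record plug status (in place or lost) with every tear lake reading, including at Visits 2 and 3.
3. In 10.4.2, report the ITT change for all inserted eyes, as defined in 10.1, using observed off-plug readings. Where a scheduled reading is missing, let the exit reading stand in for it in a sensitivity analysis only.
4. Report a separately named plug-in-place analysis with its n at each visit.

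The cost is one extra slit-lamp micrometer reading per extruded subject, sometimes two, a plug-status field on the CRF and a few sentences of text. Subjects are not asked to attend beyond the follow-up that 5.5 already provides. The ITT change may come out smaller if plugs are lost; the plug-in-place result remains available beside it.
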